5.5.1.5. Device Success

Device success is defined as the ability to insert the Peregrine Catheter into the lumen of the renal artery [target vessel], deploy the guide tubes inside the renal artery, deploy the needles through the arterial wall, deliver the intended dose of alcohol, retract the needles and the guide tubes back in the catheter, and remove the catheter from the access site without any related complications or events. The number and percent of devices used successfully will be summarized in the treated group. Devices opened but not used (i.e. no attempt was made to insert the device into the body) will not be included in the summary. These analyses will be conducted in the ITT analysis set.

5.5.1.6. Procedure Success

Procedure success is defined as device success with freedom from peri-procedural MAEs and will be summarized at the subject level. The number and percent of subjects who experience procedure success will be summarized in the treatment group. These analyses will be conducted in the ITT Analysis Set.

5.5.2. Secondary Efficacy Endpoints

5.5.2.1. Change in Mean 24-hour, Daytime, and Nighttime Ambulatory SBP and DBP from Baseline to Time Points Post-Treatment.

The mean change in ambulatory blood pressures at all collected time points will be reported with 95% CIs as described in Section 5.6. These analyses will be conducted in the ITT and PP analysis sets.

The sensitivity analyses as proposed in Section 5.4.1 for the primary mean 24-hour SBP will be additionally conducted for the 8-week daytime and nighttime SBP.

5.5.2.2. Change in Mean Office SBP and DBP from Baseline to Time Points Post-Treatment. The mean change in office blood pressures at all collected time points will be reported with 95% CIs as described in Section 5.6. These analyses will be conducted in the ITT and PP analysis sets.

The sensitivity analyses as proposed in Section 5.4.1 for the primary mean 24-hour SBP will be additionally conducted for the 8-week office SBP.

5.5.2.3. Percentage of Subjects Controlled to Target Blood Pressure Values.

The number and percent of patients controlled to target office blood pressure of <140 and >90 mmHg will be summarized by treatment group and compared via Fisher's Exact test. These analyses will be conducted in the ITT and PP analysis sets.

5.5.2.4. Use of Antihypertensive Medication(s) from Time of Procedure to 8 weeks Post-Treatment (Emergency Use Medication).

The mean change in the number of antihypertensive medications will be summarized as described in Section 5.7 along with 95% CIs for the mean change in number of medications. The addition of new antihypertensive drugs will be considered an intensification of the antihypertensive regimen. Discontinuation of one or more of the baseline antihypertensive medications without an increase in dose of remaining drugs or addition of new drugs will be considered a reduction in antihypertensive drug regimen.

Antihypertensive dose titration will be scored according to the protocol as defined in the tables below. The mean treatment score will be reported by treatment group and the groups compared via Fisher's Exact test. These analyses will be conducted in the ITT and PP analysis sets.

Step (Target SBP <140 mmHg and ≥90 mmHg)¹	Drug	Treatment Score ²
0 (not needed)	None	0
1 (if needed)	CCB: mid-dose	1
2 (if needed)	ACE inhibitor or ARB: full dose	2
3 (if needed)	Hydrochlorothiazide 12.5 mg	3
4 (if needed)	Hydrochlorothiazide 25 mg	4
5 (if needed)	CCB: increase to full dose	5
6 (if needed)	Spironolactone or beta-blocker or clonidine	6
7 (if needed)	Spironolactone or beta-blocker or clonidine	7
8 (if needed)	Spironolactone or beta-blocker or clonidine	8

Abbreviations: ACE = angiotensin-converting enzyme; ARB = angiotensin receptor blocker; BP = blood pressure; CCB = calcium channel blocker; SBP = systolic blood pressure.

- 1. There will usually be 2 to 3 weeks between steps. If the target is reached, there are no further steps even if BP fluctuates above the target. If initial systolic blood pressure (SBP) is ≥160 mmHg, Steps 1 and 2 can be combined. Fixed-combination drug products can be used to decrease pill burden.
- 2. The treatment score will be used for the purpose of the statistical analysis.

Source: Weber et al. 2015

5.5.2.5. Use of Antihypertensive Medication(s) (including Increases/Decreases) from 8 weeks to 6 months Post-Treatment (Titrated According to Standardized Formula to Maintain a Target SBP of <140 mmHg and ≥90 mmHg).

The mean change in the number of antihypertensive medications will be summarized as described in Section 5.7 along with 95% CIs for the mean change in number of medications. The addition of new antihypertensive drugs will be considered an intensification of the antihypertensive regimen. Discontinuation of one or more of the baseline antihypertensive medications without an increase in dose of remaining drugs or addition of new drugs will be considered a reduction in antihypertensive drug regimen.

The mean treatment score will be reported by treatment group and the groups compared via Fisher's Exact test. These analyses will be conducted in the ITT and PP analysis sets.

5.5.2.6. Compliance with Not Taking Antihypertensive Medications Through 8 weeks Post-Treatment. The number and percent of patients in whom no antihypertensive medications are detected according to urine compliance results will be summarized by treatment group and compared using Fisher's Exact test. Subjects who meet the protocol defined criteria for antihypertensive drug treatment and receive treatment within 8 weeks will be excluded from the analysis. These analyses will be conducted in the ITT and PP analysis sets.

5.5.2.7. Use of Antihypertensive Medication(s) according to Defined Daily Dose.

In addition to the protocol specified analyses as described above, prescribed medications will be summarized according to the sum of the defined daily dose (DDD) in order to assess and

compare total drug consumption between groups (World Health Organization Collaborating Centre for Drug Statistics, 2019). The data will be expressed as DDD/100 patient days.

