- 11 If the renal duplex ultrasound assessment at 6 months cannot be performed, or if the results are non-diagnostic, CTA/MRA/renal angiography may be performed if agreed with the sponsor (depending upon local regulatory approvals and site capacity). If renal artery stenosis of >60% or any other significant abnormality is suspected or confirmed by renal duplex ultrasound, as evaluated by the core laboratory, or as the result of other clinical assessments, those findings should be confirmed using the imaging modality used at screening (CTA/MRA/renal angiography). The choice of imaging may be changed at the discretion of the investigator and should be discussed with the sponsor.
- 12 Subjects with an eGFR of >45 and <60 mL/min/1.73 m² based on the screening serum creatinine sample will undergo blood sampling for post-contrast serum creatinine measurement 48-96 hours after imaging at screening. Subjects with an eGFR of >45 and <60 mL/min/1.73 m² based on the Week -1 (baseline) serum creatinine sample will undergo blood sampling for post-contrast serum creatinine measurement 48-96 hours after imaging during the procedure and any subsequent procedure where imaging contrast is used.
- 13 See Table 3 for details of blood and urine parameters. Tests to be done in the case of ET will be as for the Month 6 visit, but excluding compliance tests.
- 14 For measurement of serum creatinine only (all subjects). This sample must be taken prior to imaging at screening, because the eGFR value based on this measurement will be used to assess whether the subject is excluded or may proceed to have the screening imaging assessment.
- 15 Activated coagulation time (ACT) only is performed on Day 0, per the hospital's standard of care.
- 16 For compliance testing only.
- 17 No antihypertensive medications are permitted from the start of the run-in period until the subject has completed the visit at 8 weeks post-treatment (except in the case of emergencies).
- 18 Antihypertensive medications may be given after the 8-week visit if necessary (according to pre-defined criteria and proposed titration schedule).

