- 19 Screening visit: full physical examination, height, weight, temperature, and HR. Week -2: abbreviated physical examination, weight, temperature, and HR; Week -1: temperature and HR; Day 0: single measurement of cuff BP and HR before and after study procedure (while in cath lab/special procedure lab); Day 1: abbreviated physical examination, single measurement of cuff BP, HR, and temperature; Weeks 4 and 8, and Month 3: weight, HR, and temperature; Month 6: full physical examination, weight, HR, and temperature; Years 1 and 2: weight, HR, and temperature; ET visit: abbreviated physical examination, weight, temperature, and HR.
- 20 Subjects will record BP twice daily, any antihypertensive medication(s) taken, and other notes (e.g. symptoms, illnesses). Subjects do not have to complete the subject diary during the in-hospital period.
- 21 Randomization will be performed in the cath lab/special procedure lab after the subject has been sedated and after renal angiography.
- 22 Questionnaire to be conducted post-treatment (>4 hours and <24 hours).
- 23 All AEs must be recorded from the time of signing the informed consent form through the end of study participation.
- 24 All medications (prescribed or over-the-counter, including supplements) must be recorded from the time of signing the informed consent form through the 6-month follow-up visit (or time of early termination from the study, if prior to 6 months). All antihypertensive medications must be recorded starting from the time of signing the informed consent form through the 2-year follow-up visit (or time of early termination from the study). In addition, all medications (prescribed or over-the-counter, including supplements) taken within 14 days prior to the onset of a serious AE (SAE) or major AE (MAE), as well as during the SAE or MAE timeframe, must be recorded starting from the time of signing the informed consent form through the 2-year follow-up visit (or time of early termination from the study).
- 25 Crossover from the Sham Control Arm to the Treatment Arm may be allowed, at the discretion of the treating investigator, after the Data Safety Monitoring Board (DSMB) has reviewed the 1-year data from all subjects and the study has been unblinded.

Table 2 Schedule of Study Assessments (Crossover Phase)

Period	Re-Screening Period	In-Hospital Period		Follow-Up Period			ET ¹
Visit Time Point	Up to Wk -4	D 0 ²	D 1	D 2 to D 4 (48-96 h) ³	Wk 4	Mth 6	
Visit Window					+/-7 D	+/-4 Wk	

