3.4.2. Secondary Efficacy Endpoints

Secondary efficacy endpoints include:

- Change in mean 24-hour ambulatory diastolic blood pressure (DBP) from baseline to 8 weeks
- Change in mean 24-hour ambulatory SBP and DBP from baseline to 6 months and 1 year
- Change in mean daytime (07:00 to 21:59) ambulatory SBP and DBP from baseline to 8 weeks, 6 months, and 1 year
- Change in mean nighttime (22:00 to 6:59) ambulatory SBP and DBP from baseline to 8 weeks, 6 months, and 1 year
- Change in mean office SBP and DBP from baseline to 8 weeks, 6 months, 1 year, and 2 years
- Percentage of subjects controlled to target blood pressure values.
- Use of antihypertensive medication(s) from time of procedure to 8 weeks post-treatment (emergency use medication).
- Use of antihypertensive medication(s) (including increases/decreases) from 8 weeks to 6 months post-treatment (titrated according to standardized formula to maintain a target office SBP of <140 mmHg and ≥90 mmHg, see Section 7.2.2 of the protocol for more detail regarding medication titration).
- Compliance with not taking antihypertensive medications, as assessed by blood and urine testing, through 8 weeks post-treatment.

3.4.3. Secondary Safety Endpoints Secondary safety endpoints include:

- Major adverse events (MAEs) through 30 days post-treatment, as adjudicated by the Clinical Events Committee (CEC). A MAE is defined as any of the following:
 - o All-cause death
 - o End-stage renal disease (ESRD) (eGFR <15 mL/min/1.73 m² or need for renal replacement therapy)
 - Significant embolic event resulting in end-organ damage or requiring intervention to prevent it
 - Major vascular complications, including major renal artery dissection, renal artery aneurysm or pseudoaneurysm that required intervention or led to renal artery stenosis (>60% diameter stenosis)
 - o Major bleeding related to renal denervation within the renal arteries, or related to the Peregrine Catheter when in the body (per protocol bleeding definition)
 - Significant acute (post-procedural) renal artery stenosis (>60% diameter stenosis) as indicated by the renal angiogram post renal denervation, and confirmed by the angiography core laboratory, which led to one of the following: (i) acute kidney injury per modified Risk, Injury, Failure, Loss of kidney function, and End-stage kidney disease (RIFLE) definition, as confirmed by renal function blood test, or (ii) percutaneous intervention.
 - Hypertensive crisis (hypertensive emergency only)

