5.2. General Considerations

5.2.1. General Methods

Two unblinded team members (either two statisticians or a statistician and a statistical programmer) will be assigned for all analyses. This will allow for discussion of output and direct QC of statistical programming on the exact same dataset.

In general, continuous variables will be summarized with descriptive statistics (n, mean, SD, range, median, and interquartile range). The difference between groups will be presented and the normal approximation will be used to calculate two-sided 95% confidence intervals (CIs). Change from baseline, when relevant, will be computed as the paired mean difference and 95% CI of the mean difference at each time point.

For all continuous primary and secondary blood pressure endpoints, changes over time will be additionally explored in mixed effects repeated measures analyses, including the values at all time points.

Categorical variables will be summarized as frequencies and percentages. Relative risks and 95% CIs will be computed.

All statistical analyses will be performed using SAS® Version 9.4 or higher (SAS Institute, Cary, NC 27513, USA).

For each variable, the baseline value will be defined as the last value collected before the procedure.

There will be no formal hypothesis testing conducted in the study. Ninety-five percent CIs, when presented, are intended to be descriptive in nature only. For binary variables, CIs will be calculated via exact binomial methods. For continuous variables, the CI of the mean will be constructed using the normal approximation.

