5.7. Antihypertensive Medications

The mean number of antihypertensive medications will be summarized at baseline, 8 weeks, 6 months, 1 year and 2 years. The number and percentage of patients on 0 to 3, and >3 medications will additionally be presented. The mean change from baseline in the number of antihypertensive medications at each visit will be presented along with the matched baseline mean values. Antihypertensive medications will also be summarized by class. These analyses will be conducted in the ITT Analysis Set.

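### SAP 5.5.2.4 reports emergency drug use over the first 8 weeks through a drug count at the 8-week visit, so a rescue drug started and stopped before that visit scores zero

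*SAP*

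**What the plan says.** SAP 3.4.2 defines the endpoint over a period: "Use of antihypertensive medication(s) from time of procedure to 8 weeks post-treatment (emergency use medication".

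SAP 5.5.2.4 gives the derivation: "The mean change in the number of antihypertensive medications will be summarized as described in Section 5.7". It adds three things: adding a drug counts as intensification, stopping a baseline drug without compensation counts as reduction, and a mean treatment score is reported by group.

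SAP 5.7 fixes when the count is taken: "The mean number of antihypertensive medications will be summarized at baseline, 8 weeks, 6 months, 1 year and 2 years". It fixes the change variable too: "The mean change from baseline in the number of antihypertensive medications at each visit will be presented along with the matched baseline mean values".

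SAP 5.2.1 sets the reference value: "For each variable, the baseline value will be defined as the last value collected before the procedure".

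The footnotes to the protocol's Table 1 (main-study schedule) give the treatment rules. Emergencies apart, "No antihypertensive medications are permitted from the start of the run-in period until the subject has completed the visit at 8 weeks post-treatment" (footnote 17). Then, "Antihypertensive medications may be given after the 8-week visit if necessary" (footnote 18). Footnote 24 secures the raw data: "All antihypertensive medications must be recorded starting from the time of signing the informed consent form through the 2-year follow-up visit".

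**The concern.** The endpoint asks whether a subject needed drug at any time in an interval. The derivation looks at the two ends of that interval and takes the difference. The two agree only for subjects whose rescue drug is still running at the 8-week visit.

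The counting, intensification and reduction sentences in 5.5.2.4 also appear in 5.5.2.5, which covers titration from 8 weeks to 6 months. A visit-to-visit change suits titration. It suits a drug-free period poorly: reduction, for instance, cannot occur in a subject whose baseline count is zero.

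Rescue in the drug-free period is the trial's treatment-failure signal. Four of the five additional analyses listed in SAP 5.4.1, and the exploratory win ratio, depend on whether drug was received within 8 weeks. The secondary endpoint meant to report rescue by arm could show little or none while those analyses remove, impute or rank down the same subjects.

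**Working it through.** The plan states no figure for emergency drug use, so there is none to reproduce. The check is a reading of 5.5.2.4 against 5.7, followed by an illustration.

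**What the rule gives for one subject**

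Change = drugs at the 8-week visit − drugs at baseline. Baseline = 0 after a compliant run-in (SAP 5.2.1; protocol Table 1, footnote 17).

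- Never rescued: 0 − 0 = 0.
- Emergency drug on days 10 to 17, then stopped: 0 − 0 = 0.
- Emergency drug from day 40, continued through the visit: 1 − 0 = +1.

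The first two subjects differ on the endpoint but not on the derived variable.

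**What the rule gives for two arms**

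Inputs: n = 45 per arm (SAP 3.3). Assumed, because the documents are silent: r rescued subjects per arm, one drug each, and a share s of them off drug before the visit, with s equal in both arms.

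- Interval measure per arm = r / n
- Mean change in count per arm = r(1 − s) / n

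| Assumed rescued, treatment vs sham | Interval measure | Difference | Count difference, s = 0 | s = 0.5 | s = 1 |
|---|---|---|---|---|---|
| 2/45 vs 7/45 | 4.4% vs 15.6% | −11.1 points | −0.111 | −0.056 | 0.000 |
| 4/45 vs 10/45 | 8.9% vs 22.2% | −13.3 points | −0.133 | −0.067 | 0.000 |

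With s = 0 the count carries the whole difference; with s = 1 it carries none.

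**The boundary at the 8-week visit**

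The ban ends on completion of the visit, and routine drugs may follow. Protocol Table 1 marks both in the Week 8 column. Section 5.7 does not say whether its 8-week count is taken before or after a drug started that day. If such drugs were counted, each arm would gain (n − r)q / n, where q is the assumed share of non-rescued subjects starting one drug at the visit. Take 2/45 vs 7/45 with s = 1:

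- q = 30% in both arms: 43 × 0.3 / 45 = 0.287 vs 38 × 0.3 / 45 = 0.253, difference +0.033.
- q = 30% vs 50%: 0.287 vs 38 × 0.5 / 45 = 0.422, difference −0.136.

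These show what an unstated cut-off could do. They do not predict what the programmers would do.

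**Whether another planned summary reports any use in the interval by arm**

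- Treatment score and intensification (5.5.2.4): no assessment time, no rule such as highest value in the interval, and no Week 8 cut-off.
- Compliance (5.5.2.6): leaves out subjects treated under the protocol criteria.
- Defined daily dose (5.5.2.7): no 8-week window and no restriction to emergency use.
- Rescue status in 5.4.1: used to handle the blood pressure data and in the win ratio, not tabulated as an endpoint.

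None clearly does.

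**The case against.** The strongest reply is that the count is one of several summaries in 5.5.2.4. The section heading limits it to emergency use between procedure and 8 weeks. Read under that heading, a drug taken on days 10 to 17 is an added drug and so an intensification. This reading is reasonable and weakens the point. It does not remove it, because the interval has to be inferred from the heading, while the only timing rule actually written is the visit-based one in 5.7.

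The table shells in Appendix A belong to the plan but are not in the text available here. Table 14.2.6-1 is titled for emergency use medications, and its shell may contain an any-use row. The point is therefore limited to the SAP's prose.

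Rescue status is needed elsewhere too (5.4.1, 5.5.2.6 and the per-protocol definition in 4.1), and every antihypertensive is listed in Listing 16.2.9-1. So the information is not lost to the trial. What is missing is a clear rule for reporting it as this endpoint.

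Two stronger readings are tempting. A reader might infer that most rescue courses would go uncounted. The documents do not support this, because they give no course length, start-time distribution or rate. A reader might also infer that planned post-Week-8 titration will be counted as rescue. Protocol footnotes 17 and 18, the heading of 5.5.2.4, and the separate tables for emergency use (14.2.6) and use beyond 8 weeks (14.2.7) all point the other way. What stands is only that the same-day cut-off is unwritten.

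**Conclusion.** The mismatch holds on the text. Applied as written, the Section 5.7 change gives 0 to a subject rescued and off drug again by the 8-week visit, and no other summary in the SAP's prose clearly corrects this. This rests on a baseline count of zero. If baseline were instead read as the regimen of 0 to 2 drugs before the run-in, the change could be negative, but SAP 5.2.1 points to the pre-procedure value.

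The size cannot be determined from the documents. The loss runs from nil, if every rescue drug is continued to Week 8, to total, if all are stopped before it; the tabulated rates are illustrations only.

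The consequence is bounded. The endpoint is supportive, the SAP plans no formal hypothesis testing, and the primary analysis does not use this variable. It is worth correcting because the stated rule can give a wrong answer to the question the endpoint asks.

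**What to change.** In SAP 5.5.2.4, add as the main summary the number and percent of subjects in each arm with any antihypertensive use after the procedure and before completion of the 8-week visit assessments.

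- **Subjects with no 8-week visit:** run the interval to the end of the 8-week analysis window (day 86, SAP 5.2.8) or to withdrawal.
- **Source:** the dated medication log. Start and stop dates are already collected for the listing in SAP 5.13.
- **Boundary:** exclude drugs first taken after the 8-week assessments.
- **Comparison:** Fisher's exact test, with the relative risk and 95% CI that SAP 5.2.1 already prescribes for categorical variables.
- **Also report:** the number of distinct drugs used in the interval.

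Keep the Section 5.7 visit counts, including the one at 8 weeks, which 5.5.2.5 needs as its starting point.

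The cost is SAP wording and one table. No new data are needed and patient management does not change.

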- 2 At a screening visit, after written informed consent has been provided, initial screening assessments will be made. Subjects will then attend for magnetic resonance angiography (MRA) to assess renal vasculature before the start of the run-in period. For sites that would prefer to use computed tomography angiography (CTA) instead, agreement may be reached with the sponsor on a case-by-case basis (depending upon local regulatory approvals and site capacity). Subjects must have an estimated glomerular filtration rate (eGFR) of >45 mL/min/1.73 m² confirmed before imaging at screening. Subjects who are currently taking antihypertensive medications will down-titrate their medications, if necessary, so that they are taking 0 antihypertensive medications at the start of the run-in period.
- 3 Subjects will take 0 antihypertensive medications from the start of the run-in period (Week -4). During the run-in period, a safety visit will take place approximately 2 weeks before the procedure (Week -2). Further study assessments and a final check of eligibility criteria will be performed approximately 1 week before the procedure (Week -1), including office blood pressure and ambulatory blood pressure monitoring (ABPM) measurements.
- 4 Subjects may be admitted on Day -1 for logistical reasons. For the day of the procedure (Day 0), flexibility in scheduling is permitted (up to 1 week), e.g. due to cath lab availability, based on physician discretion and with careful consideration of subject safety. Randomization 1:1 (Treatment Arm : Sham Control Arm) will be performed in the cath lab/special procedure lab on the day of the procedure (Day 0), after the subject has been sedated and undergone diagnostic renal angiography.
- 5 Subjects will continue to use 0 antihypertensive medications during the first 8 weeks after the procedure (except for emergencies). After 8 weeks, antihypertensive medications are permitted, if necessary (see Appendix I).
- 6 Study unblinding will be performed after the last subject has completed the 1-year follow-up visit.
- 7 Crossover from the Sham Control Arm to the Treatment Arm may be allowed, at the discretion of the treating investigator, after the Data Safety Monitoring Board (DSMB) has reviewed the 1-year data from all subjects and the study has been unblinded.

Figure 2 Study Flow Diagram: Subject Screening, Run-in, and Treatment

BP = blood pressure; DBP = diastolic blood pressure; N = number of subjects; SBP = systolic blood pressure

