Appendix I Proposed Structured Drug Titration

After 8 weeks post-treatment, subjects may take antihypertensive medications to maintain a target office SBP of <140 mmHg and ≥ 90 mmHg (based on a mean of 3 measurements). The titration regimen provided in the following table should be followed if possible.

Step (Target SBP <140 mmHg and ≥ 90 mmHg) ¹	Drug	Treatment Score
0 (not needed)	None	0
1 (if needed)	CCB: mid-dose	1
2 (if needed)	ACE inhibitor or ARB: full dose	2
3 (if needed)	Hydrochlorothiazide 12.5 mg	3
4 (if needed)	Hydrochlorothiazide 25 mg	4
5 (if needed)	CCB: increase to full dose	5
6 (if needed)	Spironolactone or beta-blocker or clonidine	6
7 (if needed)	Spironolactone or beta-blocker or clonidine	7
8 (if needed)	Spironolactone or beta-blocker or clonidine	8

Abbreviations: ACE = angiotensin-converting enzyme; ARB = angiotensin receptor blocker; BP = blood pressure; CCB = calcium channel blocker; SBP = systolic blood pressure.

1 There will usually be 2 to 3 weeks between steps. If the target is reached, there are no further steps even if BP fluctuates above the target. For Steps 6, 7, and 8, the choice of drug and dose is at the investigator's discretion. If initial systolic BP is ≥ 160 mmHg, Steps 1 and 2 can be combined. Fixed-combination drug products can be used to decrease pill burden.

Source: Weber MA, Kirtane A, Mauri L, et al. Renal denervation for the treatment of hypertension: making a new start, getting it right. *J Clin Hypertens* 2015;17(10):743-50.

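### SAP 5.5.2.4 scores emergency drug use in Weeks 0–8 on the post-Week-8 titration ladder, so the mean score mixes how many subjects were rescued with which drug and dose they received

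*SAP*

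**What the plan says.** SAP 3.4.2 lists as a secondary efficacy endpoint "Use of antihypertensive medication(s) from time of procedure to 8 weeks post-treatment (emergency use medication". For this endpoint SAP 5.5.2.4 plans three things:

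- the mean change in number of antihypertensive drugs with a 95% CI, as described in SAP 5.7;
- a classification of regimens as intensified or reduced;
- a treatment score, introduced by "Antihypertensive dose titration will be scored according to the protocol as defined in the tables below".

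The score table gives 0 for no drug, 1 for a mid-dose CCB, 5 for a full-dose CCB, 3 or 4 for hydrochlorothiazide by dose, and 6, 7 and 8 for three rows with one and the same entry, "Spironolactone or beta-blocker or clonidine". The analysis is then: "The mean treatment score will be reported by treatment group and the groups compared via Fisher's Exact test".

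The ladder comes from Protocol Appendix I, which opens "After 8 weeks post-treatment, subjects may take antihypertensive medications to maintain a target office SBP of <140 mmHg and ≥ 90 mmHg". Both documents note that "There will usually be 2 to 3 weeks between steps". Before the Week 8 visit the protocol permits no antihypertensive drug except in emergencies, and the notes to its Figure 1 put every subject on zero drugs from the start of the run-in. SAP 5.5.2.5 applies the same score, with the same test, to Week 8 through Month 6.

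**The concern.** The ladder describes stepwise titration toward an office SBP target. In Weeks 0–8 there is no titration, only isolated emergency treatment. Each rescued subject is therefore weighted from 1 to 8 according to the row in which the drug happens to stand.

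The need for rescue is informative in an off-medication trial. In addition, sensitivity analyses 1, 2 and 5 of the primary endpoint (SAP 5.4.1) depend on which subjects met the criteria and were treated, so a reader needs the rescue rate by arm to interpret them. A mean ladder score does not supply it, and it can differ between arms with equal rescue rates or agree between arms with unequal ones.

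**Working it through.** **Inputs.** Scores 0 to 8: SAP 5.5.2.4. Arm size 45: SAP 3.3. The documents give no expected rescue rate and no figure for the score, so there is no stated result to reproduce. All rescue counts below are assumptions for illustration.

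**Formula.** A subject without a drug scores 0. Hence

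mean score = (number rescued / 45) × (mean step among those rescued).

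The first factor is the rescue rate. The second depends on drug and dose.

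**Results.** The last column is a two-sided Fisher's exact test on rescued yes/no.

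| Case | Arm A | Arm B | Mean score A | Mean score B | Fisher p |
|---|---|---|---|---|---|
| 1 | 4 at step 1 (8.9%) | 4 at step 6 (8.9%) | 4×1/45 = 0.089 | 4×6/45 = 0.533 | 1.0 |
| 2 | 1 at step 8 (2.2%) | 8 at step 1 (17.8%) | 1×8/45 = 0.178 | 8×1/45 = 0.178 | 0.030 |
| 3 | 1 at step 6 (2.2%) | 6 at step 1 (13.3%) | 1×6/45 = 0.133 | 6×1/45 = 0.133 | 0.11 |
| 4 | 4 at step 6 (8.9%) | 4 at step 8 (8.9%) | 4×6/45 = 0.533 | 4×8/45 = 0.711 | 1.0 |
| 5 | 1 at step 1 (2.2%) | 6 at step 1 (13.3%) | 1×1/45 = 0.022 | 6×1/45 = 0.133 | 0.11 |

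Case 1 shows a six-fold difference in mean score at equal rescue rates. Cases 2 and 3 show equal mean scores at unequal rates. In case 4 both arms may have received the same drugs, and only the row chosen differs. Case 5 shows that when the step is the same in both arms, the score does follow the number rescued.

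**Is the score defined for one emergency drug?** Not always. A drug from the list shared by steps 6 to 8 could score 6, 7 or 8, and a drug not on the ladder has no score. Nor would titration usually reach those rows in this period: steps 1 to 6 span five intervals of 2 to 3 weeks, or 10 to 15 weeks; with steps 1 and 2 combined, as the ladder allows from an initial SBP of 160 mmHg, four intervals take 8 to 12 weeks.

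**Does the test match the summary?** Fisher's exact test works on counts in categories. It suits rescued yes/no, but it does not compare mean scores.

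**Can a reduction occur?** SAP 5.2.1 defines baseline as the last value before the procedure, when subjects are on zero drugs, so no baseline drug can be discontinued. If baseline meant the drugs taken at enrollment, the washout that the protocol requires would itself count as a reduction. Neither reading is informative.

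**The case against.** The strongest reply is that the score is only one of several summaries and that rescue is covered elsewhere.

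- **Mean change in number of drugs (5.5.2.4, via 5.7).** With zero drugs at baseline and one rescue drug per rescued subject still in use at Week 8, this equals the proportion rescued. In case 1 it would be 4/45 = 0.089 in both arms. This stands, with a limit: 5.7 counts at visits, so a drug stopped before Week 8 can be missed, and a subject on two drugs counts twice.
- **Counts by number of drugs (5.7).** Planned at 8 weeks, but the band of 0 to 3 drugs, read literally, does not separate none from one.
- **Hierarchical analysis (5.4.1).** It uses rescue yes/no as its first tier, but it is exploratory and merges rescue with the change in SBP.
- **Compliance analysis (5.5.2.6).** It excludes subjects who met the criteria and were treated.
- **Tables 14.2.6-1 to 14.2.6-3.** They are devoted to emergency use. Their shells are not shown, so they may contain the number and percent rescued; this cannot be determined.
- **General rule (5.2.1).** It provides frequencies, percentages and relative risks for categorical variables, but 5.5.2.4 does not name rescue as such a variable.

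Two further replies stand. The physicians who perform follow-up are blinded, so no systematic difference in drug choice between arms is expected, and cases 1 and 2 are chance extremes. The endpoint is worded as use of medication and is not defined as a proportion.

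A reader might infer that the score says nothing about how many subjects were rescued, or that it merely records drug class. The score table supports neither. Untreated subjects score 0, so the mean rises with the number rescued (case 5), and the score follows drug and dose: a CCB scores 1 or 5, hydrochlorothiazide 3 or 4.

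**Conclusion.** The point holds as a misfit between a stated scoring rule and its endpoint. The Week 0–8 mean score confounds the rescue rate with the ladder step, is not uniquely defined for some drugs, and is paired with a test that does not compare means. None of the other planned summaries, as far as the SAP text shows, is a between-arm comparison of the proportion rescued.

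The numerical examples show what the score can do and are not a forecast; they rest on assumed counts, 45 per arm, and reading the score table as a look-up from drug to score. It would go too far to conclude that the SAP ignores rescue. The severity is minor: the endpoint is secondary and supportive, SAP 5.2.1 plans no formal hypothesis testing, and the primary analysis does not use the score.

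**What to change.** In SAP 5.5.2.4:

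- Report by arm the number and percent of subjects with any emergency antihypertensive use between the procedure and the Week 8 assessment, with Fisher's exact test, relative risk and 95% CI. List the drugs by class.
- Remove the ladder score and the reduction category.

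In SAP 5.5.2.5, keep the ladder score, since that is the period for which the ladder was written, and replace Fisher's exact test with one suited to an ordinal or continuous score, such as the Mann-Whitney U test that the SAP already uses in 5.4.1.

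Check that the shells of Tables 14.2.6-1 to 14.2.6-3 show the proportion rescued. The cost is a few lines of SAP text and the matching shells; no new data are needed, because all antihypertensive medication is recorded from consent onward.
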